 - A description of each adverse event by type, severity, time of detection (days post-application and/or post-removal) captured as date AE is diagnosed, clinical management, and resolution. The likelihood of relatedness to having undergone VMMC and relatedness specifically to the ShangRing device will be determined. AEs will be defined using the definitions in the second edition of the VMMC Adverse Event Action Guide.²⁴ These are specific to each AE type, but in general:
 - Mild: classification indicates minimal or no intervention is required beyond reassurance and observation;
 - Moderate: classification relates to those AEs that are neither mild nor severe, require intervention, and are usually managed on-site;
 - Severe: classification requires extensive intervention with referral or specialist input.
 - Note: a Serious Adverse Event (SAE) is a standard definition used across many types of interventions. In the context of VMMC, all AEs that meet criteria for severe should also be classified as SAEs. In addition, SAEs also include any event that:
 - Results in death

- Is life threatening
- Requires intervention to prevent permanent disability or incapacitation (including deformity), or results in permanent disability or incapacitation (including deformity)
- Requires hospitalization or referral to a specialist for higher level care or intervention.
- (Note: device displacement is included as an AE both in the moderate and severe classifications – see Appendix XV).

Secondary Endpoints

- Determine the training needed for proficiency, including number of procedures required under supervision to become certified as fully proficient. This will involve analyzing AE rates stratified by during training and post-training in addition to overall.
 - Determining whether various cadres are trainable as safe providers. This would involve analyzing AE rates stratified by provider cadre.
- Document client acceptability and satisfaction, to be measured by the following:
 - Time for client to return to normal activity, including work and routine tasks.
 - Clients' opinions of convenience (having device applied, 'wearing' the device for a week, and returning for device removal), acceptability, cosmetic result, and whether they would recommend VMMC, and specifically the ShangRing VMMC option to others.

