Data from the client's surgical and male circumcision medical records will be recorded on CRFs included in the Appendices (see Appendices VII and IX). The CRFs will be used to transfer the information collected in the performance of this evaluation to the clinical database. The original CRF will be kept in the clinic files and a copy will be maintained with additional documentation specifically for this evaluation including photographs, interviewer administered surveys and brief questionnaires. The hardcopy data will be entered into the evaluation database at each site. Corresponding forms, surveys and questionnaires will be completed immediately after each subject's visit. The site coordinator will review the CRFs for completeness and accuracy (signatures, dates, adverse events, serious adverse events, protocol departures) sign/date the forms where indicated. The evaluation team will retain originals of all source documents, subject consent forms, photographs and evaluation data as a permanent record.

The following data will be collected from clients receiving ShangRing circumcision:

Clinic Visit #1: Enrollment and Circumcision (Day 0)

- Documentation of general physical screening and medical examination on CRF
- Documentation of medication history on CRF
- Documentation of genital examination on CRF
- Documentation of device-related events and AE on forms, as needed
- Administration of evaluation survey after circumcision
- Collection of contact information from the client

Clinic Visit #2: Removal Visit (Day 7)

- Photographs of genitals after device removal
- Documentation of wound healing and genital examination on CRF
- Documentation of device-related events, AE and treatment and resolution of AE, as needed, on forms
- Documentation of changes to medical condition and medication on CRF
- Administration of evaluation survey after device removal

AE Assessment Phone Call (Day 10)

- Administration of an interview to determine whether client is experiencing signs and symptoms of an AE

Follow-Up In-Person Qualitative Interview (Day 28)

- For 50 clients
- Interview to determine client's feelings about ShangRing circumcision experience

Follow-Up In-Person Healing Assessment (Day 49)

- Documentation of wound healing and genital examination on CRF
- Photographs of genitals to document healing
- Documentation of device-related events, AE and treatment and resolution of AE, as needed, on forms

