Client acceptability, time to return to normal activity, and clients' satisfaction with the post-circumcision cosmetic results will be summarized from data recorded on the evaluation surveys and during qualitative interviews conducted with 10% of randomly selected clients. Similarly, provider acceptability will be summarized from data recorded during qualitative interviews conducted with providers. Qualitative interviews will be digitally recorded and then transcribed by qualified staff. The recordings will be transcribed according to the local language used and then to English. The recordings will not be marked with any identifying information but with a unique identifier. Transcriptions will be reviewed electronically, using a qualitative interview analysis software such as Atlas.ti or NVivo, and analyzed for themes. The analysis of the qualitative data will be done through an inductive process where categories are identified as they emerge. Opinions generated by the 10% of clients included in the interviews will be used to tailor the messaging for future program implementation.

The percentage of men healed by day 49, and the time at which all clients are healed, will be reported from data recorded on the client CRFs. The proportion of men unsuitable for ShangRing MC will be extracted from an evaluation log maintained for the purpose of documenting the number of ineligibles and the reasons for their exclusion. Similarly, the number of men who decline ShangRing or who withdrawal will be reported as a proportion.

The photographs taken to document healing and adverse events will be used to supplement the analysis of both endpoints. Photographs will be reviewed only by evaluation project staff, and used to enhance the understanding of different adverse events and as evidence of the duration of the healing process. Photographs of all adverse events (if the client consents) will also accompany the AE reporting, to provide further clarity on these events. The photos will also be used by project staff to better educate ShangRing providers.

Long-Term Data Storage

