Appendix X – ShangRing Post-Placement Survey

ShangRing Post-Placement Survey

[Table to be completed by Evaluation Staff]

Date (dd/mm/yyyy):	
Client ID:	
Name of Survey Administrator:	
Facility:	

Introduction: Thank you for agreeing to complete this survey to evaluate your experience with the ShangRing circumcision device. This survey asks a few brief questions about your experience in having the ShangRing device placed. Your name will not be recorded anywhere on this survey, and your replies will be kept completely confidential. In this survey there are no right or wrong answers. We are most interested in your honest opinions and reactions to these questions. You may also refuse to answer any question you wish for any reason. The information that you provide will help to determine the future use of ShangRing in Tanzania. If you have any questions about the survey, please do not hesitate to follow up with evaluation staff. If you have difficulty reading or understanding any of the questions, evaluation staff are on hand to read and help you interpret the questions.

1. Why did you choose to have a ShangRing circumcision instead of surgical circumcision (circle answer option below)?

I thought ShangRing would be less painful	I didn't want an injection	I had heard about ShangRing before	No Reason	Other (comment below)
Comment: _____				

2. How did you find the placement process for the ShangRing device (circle answer option below)?

It was about what I expected	It was easier than I expected	It was harder than I expected	I did not have any expectations for the placement	Other (comment below)
Comment: _____				

3. How did you find the pain of your circumcision during the ShangRing device placement (circle answer option below)?

It was about what I expected	It was less painful than I expected	It was more painful than I expected	I did not have any expectations about pain	Other (comment below)
Comment: _____				

4. At this point, would you recommend the ShangRing to someone you know who is considering circumcision (circle answer option below)?

Yes	No	I don't know at this time	Other (Comment below)
-----	----	---------------------------	-----------------------

Comment: _____

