Appendix XI – ShangRing Post-Removal Survey

ShangRing Post-Removal Survey

[Table to be completed by Evaluation Staff]

Date (dd/mm/yyyy):	
Client ID:	
Name of Survey Administrator:	
Facility:	

Introduction: Thank you for agreeing to complete this survey to evaluate your experience with the ShangRing circumcision device. This survey asks a few brief questions about your experience with ShangRing now that the device has been removed. Your name will not be recorded anywhere on this survey, and your replies will be kept completely confidential. In this survey there are no right or wrong answers. We are most interested in your honest opinions and reactions to these questions. You may also refuse to answer any question you wish for any reason. The information that you provide will help to determine the future use of ShangRing in Tanzania. If you have any questions about the survey, please do not hesitate to follow up with evaluation staff. If you have difficulty reading or understanding any of the questions, evaluation staff are on hand to read and help you interpret the questions.

1. How much discomfort did you experience while wearing the ShangRing device over the past seven days (circle answer option below)?

I had no discomfort while wearing the ring	I had minor discomfort while wearing the ring	I had moderate discomfort while wearing the ring	I had a lot of discomfort while wearing the ring	Other (comment below)
--	---	--	--	-----------------------

Comment: _____

2. How much did the ring affect you while performing day-to-day activities (circle answer option below)?

It did not affect me at all	It only affected me while performing certain activities	It affected me during all activities, but I could still do them	It prevented me from performing certain activities	Other (comment below)
-----------------------------	---	---	--	-----------------------

Comment: _____

3. After having worn the ring for a week, would you still choose to do ShangRing for circumcision, or would you choose surgery (circle answer option below)?

I would definitely choose ShangRing again	I would probably choose ShangRing again	I would probably choose surgery	I would definitely choose surgery	I don't know
---	---	---------------------------------	-----------------------------------	--------------

Comment: _____

(Survey is continued on next page)

4. How satisfied are you with the appearance of your circumcision (circle answer option below)?

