Appendix XIV – ShangRing Adverse Event Day 3 Post-Removal AE Check-in Call Form

ShangRing Adverse Event Check-in Call Form

Client ID:

Instructions

This form is to be used during the call with clients to check for signs of adverse events three days following the removal of the ShangRing device. The questions below are meant to evaluate whether the client is potentially experiencing an adverse event in the aftermath of their circumcision. After introducing yourself, and informing the client of the purpose of the call, ask the client each question on the list. For any 'yes' answers, probe for more information. If any of the information the client offers suggests an adverse event, advise that the client come to the clinic immediately for further evaluation.

Questions

1. Are you experiencing pain that keeps you from doing anything you normally do? **Y** **N**

a. **If yes:** Advise the client to visit the clinic to be evaluated

Note any comments: _____

2. Has swelling, tenderness or pain around the wound gotten worse since your circumcision? **Y** **N**

a. **If yes:** Advise the client to visit the clinic to be evaluated

Note any comments: _____

3. Have you noticed any expanding redness around the wound area, or red streaking spreading from the wound? **Y** **N**

a. **If yes:** Advise the client to visit the clinic to be evaluated

Note any comments: _____

4. Have you noticed any pus or fluid coming from the wound area? **Y** **N**

a. **If yes:** Advise the client to visit the clinic to be evaluated

Note any comments: _____

5. Have you felt like you have had a fever in the past few days, or experienced chills, shaking, breaking into sweats more than usual? **Y** **N**

a. **If yes:** Advise the client to visit the clinic to be evaluated

Note any comments: _____

6. Are you still bleeding from the wound area? **Y N**

a. **If yes:** Advise the client to visit the clinic to be evaluated

Note any comments: _____

7. Are you experiencing any difficulty urinating? **Y N**

a. **If yes:** Advise the client to visit the clinic to be evaluated

Note any comments: _____

8. Are you experiencing any other new problems since the surgery? **Y N**

a. **If yes:** Ask the client to describe the symptoms, and record below. If the symptoms are concerning advise the client to visit the clinic to be evaluated.

Note any comments: _____

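### Time to return to normal activity is a secondary measure, but no item in the surveys or interview guide named as its source records it

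*Protocol*

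**What the plan says.** Under Secondary Endpoints, the first listed measure of client acceptability and satisfaction is "Time for client to return to normal activity, including work and routine tasks".

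The Analysis Overview fixes the data source. It groups "Client acceptability, time to return to normal activity" with satisfaction with the cosmetic result and states that these "will be summarized from data recorded on the evaluation surveys and during qualitative interviews conducted with 10% of randomly selected clients".

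The Data Collection section schedules two client surveys. One is on day 0 ("Administration of evaluation survey after circumcision") and one on day 7 ("Administration of evaluation survey after device removal"). It lists no later client survey. The interviews are on day 28 with 50 clients, who must be 18 or older (In-Person Qualitative Interviews). The surveys and the interview guide are printed as Appendices X, XI and XXII.

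**The concern.** The measure is a time, so it needs a date or a day count from each client. The instruments named as its source contain neither.

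The Introduction names loss of time from work as one of two main concerns that devices may address, and suggests that an earlier return to work could help persuade men. The Justification for Evaluation says the results will inform pre-procedure counselling messages. If the forms are used as printed, the pilot can say nothing quantitative about local return to work. The report would then have to omit a stated measure or rebuild it from remarks by a small subset.

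**Working it through.** There is no stated figure to reproduce. The check is an item-by-item reading of the named sources, then of the other client forms shown.

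**Named sources**

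| Instrument | Given | Items | Nearest item | Items recording a time |
|---|---|---|---|---|
| Post-placement survey (App. X) | Day 0, all clients | 4 | None: reason for choice, placement, pain, recommendation | 0 |
| Post-removal survey (App. XI) | Day 7, all clients | 5 | Item 2: "How much did the ring affect you while performing day-to-day activities" | 0 |
| Client interview guide (App. XXII) | Day 28, 50 adults | 23 | Item 11 (limits on activities during wear); item 14 (experience since removal, probed for healing) | 0 |

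Total: 4 + 5 + 23 = 32 items, of which 0 record when activity resumed.

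The day 0 survey comes before any return to activity can be observed. Item 2 of the day 7 survey gives graded answers from no effect to being prevented from certain activities. That is a degree of interference while the ring is worn, with no day attached and no mention of work. Interview items 11 and 14 are open questions, and neither probe asks when work or routine tasks resumed.

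**Other client forms, not named as sources**

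- Day 10 call form (App. XIV), question 1: "Are you experiencing pain that keeps you from doing anything you normally do". This is a yes/no on current limitation from pain, with no time.
- Screening form, national client form, device form and follow-up form (Apps. VII, VIII, IX, XII): no field on return to activity.
- Adverse event forms (App. XVIII): no field for days of lost activity. Days of disability appear only in the grading definitions (App. XIX) and apply only to clients with an event.

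**Timing.** The last survey of all clients is on day 7, at removal. Appendix XVII advises clients against strenuous manual work, including on farms, while the ring is in place, and the protocol describes the region's economy as mainly agricultural. For manual workers who follow that advice, return to full work comes after the last survey.

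**Reach of the interviews.** 50 / 575 = 8.7% of clients, none of them aged 13–17, although enrolment starts at 13. The interview section takes the first 50 willing adults in order of enrolment, so even volunteered times would not come from a random sample.

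**The case against.** The strongest reply is that the claim is too absolute and the measure is minor.

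- **Indirect information exists.** A client who reports on day 7 that the ring did not affect him has in substance reported no interruption, and the day 10 question flags men still limited by pain. Both have comment lines. This is true, but together they give coarse categories on different things (interference during wear, current pain) and not a time.
- **The use is descriptive and qualitative.** The plan only summarises the measure, and open interviews may draw out the information. The protocol also calls its interview guides drafts. An interviewer could ask, but nothing secures it, and the ceiling is 50 adults. The draft label does not extend to the two surveys.
- **Low prominence.** The measure is absent from the executive summary's secondary endpoints and from the client acceptability entries in Table 2. Safety and healing do not depend on it. The design is single-arm, so a measured time could not show less work lost than with surgery. These points stand and limit the weight of the finding, but the gap remains.
- **Some logs are not visible.** The body of the Appendix XV follow-up log is not shown. It is not a named source, so the finding is confined to the surveys, the interview guide and the other forms that can be read.
- **Analysis is a matter for the SAP.** The choice of summary statistic may be, but an SAP cannot create a variable that was not collected, and the Analysis Overview rules out imputation.

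**Conclusion.** The concern holds. The protocol states a secondary measure and its sources, and none of the 32 items in those sources records it. By design, 0 of 575 clients would have a return-to-activity time. Ad hoc remarks could supply one for at most 50 adults.

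This rests on the instruments being used as printed and on no dated activity field sitting in a log whose body is not shown. The two surveys and the interview guide are printed in full. The point should be corrected before data collection. It does not threaten the primary safety endpoint or the healing endpoint.

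**What to change.** 1. Add to the day 10 call form two dated items: the day the client returned to work or school, and the day he returned to routine tasks. Offer the options *did not stop*, *not applicable* and *not yet*.
2. Repeat the items on the follow-up form at the day 49 visit for clients who answered *not yet* on day 10 or were not reached. This limits long recall to those who need it. The same items could also go on the day 7 survey.
3. Change the Analysis Overview to name these forms as the source, and define the time as days from placement. A median with *not yet* treated as censored would suit, with details left to the SAP. The report should note that times during wear partly reflect the activity advice given to clients.
4. If the sponsor does not want the data, delete the measure from Secondary Endpoints and the Analysis Overview.

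The cost is one or two questions at contacts already scheduled for all clients, plus the matching database fields. No extra visit and no change to clinical procedures is needed.
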